9 STUDY IMPLEMENTATION

9.1 Study Design

This is a Phase 2 study of VX-561 monotherapy. A schematic of the study design is shown in [Figure 9-1](#), which is randomized, double-blind, parallel-group, and active-controlled. The study will evaluate 4 dose levels of VX-561 in subjects with CF who have a gating mutation and were previously taking a stable dose of IVA. Randomization will be stratified by ppFEV₁ value at screening (<70 versus ≥70).

The original protocol included 25 mg once daily (qd) and 50 mg qd VX-561 treatment arms; both were discontinued in the current protocol ([REDACTED]).

Figure 9-1 VX18-561-101 Study Design

Screening 28 days	Treatment Period 12 weeks	Washout Period 3-5 days	Safety Follow-up 28 days after last dose
Enroll Subjects on Stable IVA Treatment ^a	VX-561 250 mg qd	Washout VX-561 or IVA	Resume IVA
	VX-561 150 mg qd		
	VX-561 50 mg qd (treatment arm discontinued)		
	VX-561 25 mg qd (treatment arm discontinued)		
	IVA 150 mg q12h		

^a Approximately 88 subjects were planned to enroll in 5 treatment arms (25 mg qd VX-561, 50 mg qd VX-561, 150 mg qd VX-561, 250 mg qd VX-561, and IVA 150 mg every 12 hours [q12h]) in a ratio of 1:2:2:2:1 under the original protocol. The 25 mg qd VX-561 and 50 mg qd VX-561 treatment arms were discontinued; 44 subjects had been enrolled and randomized to the 5 treatment arms at this point. The remaining subjects planned to enroll will be randomized 2:2:1 to 3 treatment arms (250 mg qd VX-561, 150 mg qd VX-561, and IVA 150 mg q12h).

9.1.1 Screening

Screening Visit assessments are listed in [Table 3-1](#).

The Screening Period will occur within 28 days before administration of study drug. Screening assessments will be used to confirm that subjects meet eligibility criteria. The investigator (or an appropriate authorized designee at the study site) will obtain informed consent from each subject before any study procedures takes place.

9.1.1.1 Repetition of Screening Assessment(s)

Screening assessments may be repeated once to establish study eligibility. If repeat values of the individual assessment(s) are within the eligibility criteria and completed within the screening window, then the subject is eligible for the study.

9.1.1.2 Rescreening

Subjects may be rescreened only once. If a subject is rescreened, all screening assessments will be repeated except for *CFTR* genotyping, follicle-stimulating hormone (FSH) level (if serum

FSH level was ≥ 40 mIU/mL during prior screening), and sweat chloride level. If a subject is rescreened, the new screening window will begin once the first rescreening assessment has been initiated.

9.1.1.3 Extension of Screening Period Window

The Screening Period window may be extended by 2 weeks for the following reasons:

- Repetition of the Screening assessments (Section 9.1.1.1)
- Unexpected operational or logistic delays, or to meet the eligibility criteria
- Repetition of spirometry assessment if results are of poor quality

9.1.2 Treatment Period

The Treatment Period will last approximately 12 weeks. Treatment Period assessments are listed in [Table 3-1](#). Dosing details are in Section 9.6.

9.1.3 Washout Period

The Washout Period will last approximately 4 days.

The study visits during the Washout Period will occur as shown in [Table 3-1](#).

9.1.4 Follow-up

Subjects will have a Safety Follow-up Visit 28 (± 7) days after the last dose of study drug. Safety Follow-up Visit assessments are listed in [Table 3-1](#).

9.1.5 Early Termination of Treatment OR Early Discontinuation

If a subject prematurely discontinues study treatment, an Early Termination of Treatment (ETT) Visit should be scheduled as soon as possible after the subject decides to terminate study treatment. Subjects who prematurely discontinue treatment will also be required to complete the Safety Follow-up Visit, approximately 28 (± 7) days after their last dose of study drug. The assessments performed at the Safety Follow-up Visit are listed in [Table 3-1](#).

Subjects who discontinue from study drug dosing for any reason (except withdrawal of consent) will have a final PK blood sample drawn as soon as possible after the decision to discontinue study drug is made. Additional safety assessments may also be performed at the discretion of the investigator, including possible consultation with a specialist consultant. The Vertex medical monitor will be informed about these additional assessments, and any additional data collected (e.g., as the result of an outside consultation) will be considered part of the study record to provide the most complete safety profile of the study drug.

If the ETT Visit occurs 3 weeks or later following the last dose of study drug, then the ETT Visit will replace the Safety Follow-up Visit, and a separate Safety Follow-up Visit will not be required.

If a subject withdraws consent for the study, no further assessments will be performed, and no additional data should be collected. Vertex may retain and continue to use any data and samples collected before such withdrawal of consent.

9.1.6 Lost to Follow-up

A subject will be considered lost to follow-up if both of the following occur:

- The subject misses 2 consecutive study visits (telephone contact and/or clinic visit) and is subsequently unable to be contacted by telephone (3 documented attempts by telephone within 2 weeks following the second missed visit).
- The subject does not respond within 2 weeks to a registered letter sent after the 3 attempted telephone contacts.

9.1.7 Independent Data Monitoring Committee

Safety and tolerability data will be reviewed by an independent data monitoring committee (IDMC) to ensure the safety of the subjects (Section 12.3.6). Procedural details of the IDMC's structure and function, frequency of meetings, and data planned for review will be in the IDMC charter. The IDMC charter will be finalized before the first subject is screened.

9.2 Method of Assigning Subjects to Treatment Groups

An interactive web response system (IWRS) will be used to assign subjects to treatment. A randomization list will be produced by Vertex Biostatistics or a qualified randomization vendor. The Vertex study biostatistician will review and approve the dummy randomization list. The final randomization list will be reviewed and approved by a designated unblinded biostatistician who is not a member of the study execution team (SET).

Subjects will be assigned a unique subject number. Only subjects who have completed screening assessments and are eligible for participation in the study will be randomized to receive study drug during the Treatment Period. Randomization will be stratified by ppFEV₁ (<70 versus ≥70) determined during screening.

Approximately 88 subjects were planned to enroll in 5 treatment arms (25 mg qd VX-561, 50 mg qd VX-561, 150 mg qd VX-561, 250 mg qd VX-561, and IVA 150 mg q12h) in a ratio of 1:2:2:2:1 under the original protocol. The 25 mg qd VX-561 and 50 mg qd VX-561 treatment arms were discontinued; 44 subjects had been enrolled and randomized to the 5 treatment arms at this point. The remaining subjects planned to enroll will be randomized 2:2:1 to 3 treatment arms (250 mg qd VX-561, 150 mg qd VX-561, and IVA 150 mg q12h).

9.3 Rationale for Study Elements

9.3.1 Study Design

Subjects will continue their stable IVA treatment through screening, and then be randomized to study drug treatment groups on Day 1 (VX-561 or IVA). The efficacy and PD of VX-561 will be assessed after 12 weeks of randomized treatment. IVA (150 mg every 12 hours [q12h]) is included as a reference arm, but with unequal randomization to provide greater information on VX-561 dose-ranging. After the Treatment Period, a 3- to 5-day Washout Period where subjects will take no CFTR modulators is included to collect additional PK and PD data and enable a more thorough evaluation of VX-561 exposure-response relationships.

Following completion of the Washout Period, subjects will resume their prior therapy with commercial IVA.

9.3.2 Study Population

The study will enroll subjects with CF with a gating mutation (see Section 8.1) to ensure a relatively homogenous population to evaluate the efficacy, PK, and PD of VX-561 across a range of doses relative to IVA.

9.3.3 Study Drug Dose and Duration

VX-561

Four dose levels of VX-561 will be evaluated to provide a broad range of exposure for exposure-response analyses. The original protocol included 25 mg qd VX-561 and 50 mg qd VX-561 treatment arms; both treatment arms were discontinued in the current protocol [REDACTED]. A VX-561 dose regimen of 150 mg qd provides exposure similar to IVA 150 mg q12h, including C_{max} , AUC_{0-24h} , and C_{trough} . Based on the similarity of VX-561 and IVA in vitro potency and efficacy in HBE cells, this dose is predicted to provide the same effect as IVA on CFTR potentiation, and thus is also expected to result in a similar PD (i.e., sweat chloride) and efficacy (i.e., ppFEV₁) response. The 250 mg qd dose of VX-561 is included to provide a range of exposures to enable a more robust exposure-response analysis.

The 12-week treatment duration is considered sufficient to avoid any carryover of the efficacy or PD effect from stable IVA treatment and avoid the need for an extended washout of IVA before the start of the Treatment Period.

IVA

The IVA dose regimen of 150 mg q12h is the approved regimen for treatment of CF in subjects aged 6 years and older who have 1 mutation in the *CFTR* gene that is responsive to IVA based on clinical and/or in vitro assay data.

9.3.4 Rationale for Study Assessments

The PK assessments and safety assessments are standard measurements for clinical studies in drug development.

The PD and efficacy endpoints being evaluated (sweat chloride and spirometry) are widely accepted and generally recognized as reliable, accurate, and relevant to the study of individuals with CF. Sweat chloride was evaluated in the registration study of IVA (Kalydeco), and spirometry was evaluated in the registration studies of IVA (Kalydeco) and LUM/IVA combination therapy (Orkambi).

9.4 Study Restrictions

Study restrictions are summarized in Table 9-1. VX-561 and IVA are metabolized extensively via CYP3A. Therefore, use of moderate and strong inducers or inhibitors of CYP3A, which have the potential to alter the exposure of VX-561 or IVA will be prohibited.

A non-exhaustive list of study prohibitions and cautions for medication will be provided in the Study Reference Manual.

Table 9-1 Study Restrictions

Restricted Medication/Food/Activity ^a	Timing of Restriction	
	Start	Stop
Moderate and strong CYP3A inducers or inhibitors (except ciprofloxacin), including grapefruit or grapefruit juice	None allowed within 14 days before the first dose of study drug	None allowed through the Safety Follow-up Visit
CFTR modulators other than study drug (e.g., Symdeko/Symkevi)	None allowed within 28 days before first dose of study drug	None allowed through the Safety Follow-up Visit

^a See Section 9.5 for guidance on concomitant medications.

9.5 Prior and Concomitant Medications

Subjects will abstain from all concomitant medications as described in the exclusion criteria (Section 8.2) and Study Restrictions (Table 9-1).

All medications taken from 28 days before the Screening Period through the end of the study will be recorded with indication, route of administration, and start and stop dates of administration. All subjects will be questioned about medications from signing of the ICF through the Safety Follow-up Visit.

- Subjects must remain on a stable CF medication (and supplement) regimen (other than protocol-specified changes in CFTR modulator regimen) for their CF from 28 days before the Day 1 Visit through the Safety Follow-up Visit. Stable CF medication regimen is defined as the current medication regimen for CF that subjects have been following for at least 28 days before the Day 1 Visit. Subjects must not initiate long-term treatment with new medication from 28 days before the Day 1 Visit through the Safety Follow-up Visit unless discussed and approved by the medical monitor.
- Subjects may receive doses of prednisone or prednisolone of up to 10 mg/day or equivalent (chronically), or prednisone or prednisolone 60 mg/day for up to 5 days, without prior approval of the medical monitor.
- Information about bronchodilator use during the study will be collected and documented. Subjects who are using a bronchodilator must have their spirometry assessments performed according to the guidelines provided in Section 11.4.

9.6 Administration

Study drug will be administered orally twice daily. Subjects will receive the same number of tablets each day to maintain the blind. Additional information is provided in the Pharmacy Manual.

Study drug will be administered with a fat-containing meal or snack, consistent with the recommendations for administration of Kalydeco¹², according to the following guidelines:

- It is recommended that the dose be taken within 30 minutes of the start of the meal or snack.
- All study drug doses will be administered q12h to maintain the blind. All doses of study drug will be taken at approximately the same time each day. For example, the morning dose could

be taken at 08:00 every morning and the evening dose could be taken at 20:00 every evening throughout the study.

- The date, amount taken, and time of study drug administration, including whether food was taken with each dose, will be recorded for the 2 doses before PK sample collection and the dose received on the morning of PK sample collection.
- On days of scheduled visits, the morning dose of study drug will be administered at the site after predose assessments have been completed. The meal or snack will be provided by the site for the morning dose of study drug.
- A subject's morning dose can be delayed by up to 6 hours to accommodate predose assessments on clinic visit days.
- For visits after the Day 1 Visit, subjects will be instructed to bring all used and unused study drug to the site; study drug will be dispensed at each visit, as appropriate.

Missed Doses

- If a subject misses a dose and recalls the missed dose within 6 hours, the subject should take the dose with food. If more than 6 hours have elapsed after the usual dosing time, the subject should skip that dose and resume the normal schedule for the following dose.

9.7 Dose Modification for Toxicity

If any unacceptable toxicity arises, individual subjects will discontinue dosing (Section 9.1.5). No dose modifications for toxicity are allowed.

9.8 Study Drug Interruption and Stopping Rules

The medical monitor should be notified of a discontinuation of study drug or an interruption of study drug that lasts >72 hours for any reason and of the resumption of study drug after such interruption.

Subjects with new treatment-emergent ALT or AST elevations of $>3 \times \text{ULN}$, or total bilirubin $>2 \times \text{ULN}$, must be followed closely, including confirmatory testing performed by the central laboratory within 48 to 72 hours of the initial finding and subsequent close monitoring of ALT, AST, and bilirubin levels, as clinically indicated.

If a subject cannot return to the site for confirmatory testing, a local laboratory may be used. Local laboratory results must be reported immediately to the medical monitor, and the subject must have the tests repeated and sent to the central laboratory as soon as possible (ideally within 48 to 72 hours).

Study drug administration **must be interrupted** immediately (prior to confirmatory testing) if any of the following criteria are met:

- ALT or AST $>8 \times \text{ULN}$
- ALT or AST $>5 \times \text{ULN}$ for more than 2 weeks
- ALT or AST $>3 \times \text{ULN}$, in association with total bilirubin $>2 \times \text{ULN}$ and/or clinical jaundice

A thorough investigation of potential causes should be conducted, and the subject should be followed closely for clinical progression.

Study drug administration **must be discontinued** if subsequent ALT or AST values confirm the initial elevation that satisfied the interruption rule (above), and no convincing alternative etiology (e.g., acetaminophen use, viral hepatitis, alcohol ingestion) is identified, regardless of whether transaminase levels have improved.

All subjects in whom treatment is discontinued for elevated transaminases and/or bilirubin should have these levels monitored closely until levels normalize or return to baseline.

If an alternative, reversible cause of transaminase elevation and/or increased bilirubin or clinical jaundice has been identified, study drug administration may be resumed once transaminases or bilirubin return to baseline or are $\leq 2 \times$ ULN, whichever is higher. Regardless of the duration of interruption, the medical monitor should be notified prior to resumption of study drug. Upon resumption of study drug, transaminases and bilirubin should be assessed weekly until the Safety Follow-up Visit. If a protocol-defined transaminase or bilirubin elevation interruption threshold recurs with rechallenge with the study drug (with confirmation of the initial elevation by repeat testing within 48 to 72 hours), then the study drug must be permanently discontinued, regardless of the presumed etiology.

Individuals who develop adverse events (AEs) will be monitored closely; consideration should be given to the need for additional safety assessments and possible consultation (e.g., with a dermatologist, GI specialist, or other specialist consultant). Any additional data collected (e.g., as a result of an outside consultation) will be considered part of the study record to provide the most complete safety profile of the study drug.

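### Read literally, the liver restart rule in Protocol 9.8 can be met, once a reversible cause is found, by a subject who still meets an interruption criterion

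*Protocol*

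**What the plan says.** Protocol 9.8 sets out three steps.

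- **Interruption.** Study drug must be interrupted "immediately (prior to confirmatory testing) if any of the following criteria are met". The criteria are (1) ALT or AST >8×ULN; (2) ALT or AST >5×ULN for more than 2 weeks; (3) ALT or AST >3×ULN together with total bilirubin >2×ULN and/or clinical jaundice.
- **Discontinuation.** Study drug must be discontinued "if subsequent ALT or AST values confirm the initial elevation that satisfied the interruption rule (above), and no convincing alternative etiology" is found. Both parts are needed.
- **Resumption.** The precondition is that an alternative, reversible cause of the transaminase elevation, raised bilirubin or jaundice has been identified. Then "study drug administration may be resumed once transaminases or bilirubin return to baseline or are" at most 2×ULN, whichever is higher. The medical monitor is to be notified before restart, and transaminases and bilirubin are then tested weekly. If an interruption threshold recurs on rechallenge and is confirmed, study drug stops permanently.

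Neither the SAP nor the readable text of the COVID-19 addenda changes or explains these rules.

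**The concern.** A rule that stops treatment and a rule that lets it restart should not both be satisfied by the same laboratory values. Here the restart sentence joins the two analytes with *or*, although two of the three triggers concern transaminases alone. An analyte that played no part in the interruption can then satisfy the restart condition.

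What is at stake is the safety of individual subjects and consistent conduct across sites. The rechallenge clause is affected too. It speaks of a threshold recurring, which presumes that the subject was below it at restart.

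There is a smaller gap alongside. Interruption comes before confirmation, so some subjects will be interrupted on a value that the repeat test does not support. If no cause is found for such a value, 9.8 does not say what happens next.

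**Working it through.** No sample size, power or error rate is involved. The check is one of logic, using the conditions in Protocol 9.8 and the screening limits in Protocol 8.2.

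**Restart limits.** Let A be the current ALT or AST and B the current total bilirubin, both in multiples of ULN. The literal restart laboratory condition is

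A ≤ max(baseline A, 2) **or** B ≤ max(baseline B, 2).

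Protocol 8.2 excludes subjects with ALT or AST ≥3×ULN or total bilirubin ≥2×ULN at screening. Assuming that baseline stays below those limits, the transaminase limit is below 3 and the bilirubin limit is 2. A subject who still meets any trigger has A > 3, so the transaminase limb fails. Any overlap must therefore come through the bilirubin limb, B ≤ 2.

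**Each trigger with B ≤ 2, a reversible cause having been identified**

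| Trigger still met | Example | Restart laboratory condition | Both met? |
|---|---|---|---|
| 1: A > 8 | A = 9, B = 0.8 | met through bilirubin | yes |
| 2: A > 5 for more than 2 weeks | A = 5.5, B = 0.8 | met through bilirubin | yes |
| 3: A > 3 with B > 2, no jaundice | needs B > 2 | not met | no |
| 3: A > 3 with jaundice | A = 3.5, B = 1.9 | met through bilirubin | yes |

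The last row arises because the restart sentence names jaundice among the findings whose cause may be identified, but does not ask that it has resolved.

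**Enumeration.** An illustrative grid used A = 1, 2, 2.5, 3.5, 5.5, 9; B = 0.8, 1.9, 2.5; jaundice yes or no; duration above 5×ULN longer than 2 weeks yes or no (only where A > 5); baseline A of 1 or 2.9; and baseline B of 0.8 or 1.9.

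- States: (4 values of A × 1 + 2 values × 2 durations) × 3 × 2 × 2 × 2 = 8 × 24 = 192.
- States meeting a trigger with B ≤ 2: A = 3.5 gives 1 (jaundice), A = 5.5 gives 3, and A = 9 gives 4, or 8 in all. Multiplied by 2 values of B and 4 baseline pairs, this is 64.
- So 64 of 192 states satisfy both restart and interruption. Replacing *or* by *and* gives 0 of 192. That locates the source of the overlap in the one word; it is not offered as the right clinical rule.

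The counts depend on the grid. They show that the overlap exists and are not probabilities.

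**Paths out of interruption under 9.8**

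| Elevation | No convincing cause | Reversible cause |
|---|---|---|
| Confirmed | discontinue | may resume when laboratory condition met |
| Not confirmed | no criterion stated | may resume when laboratory condition met |

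Discontinuation fails in the lower left cell because it needs confirmation. Resumption fails there because it needs an identified cause.

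**The case against.** The strongest reply is that the restart sentence means whichever analyte was raised. It opens with the abnormality whose cause was found, and a bilirubin that never rose cannot return to anything. On that reading the overlap under the two transaminase-only triggers disappears. The reading is natural, but no passage states it. The alternative limb, being at most 2×ULN, needs no earlier rise, so the literal reading stays open. The reading also leaves unclear what is required when both analytes were raised, and it does not deal with jaundice.

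Second, interruption is mandatory and restart only permitted, so a careful investigator would not restart while a trigger still applies. Notice to the medical monitor and weekly testing add protection. These points stand and lower the practical risk. However, the text asks for notification rather than approval, and it does not say which rule prevails.

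Three stronger readings are tempting, and the documents do not support them:

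- **Every early restart under the bilirubin limb is a contradiction.** Take ALT 6×ULN with bilirubin 3×ULN, falling to 4.5 and 1.8. The literal restart condition is met, but no trigger is: ALT is not above 8 or 5, and bilirubin is not above 2. Unless jaundice persists there is no conflict, and whether restart at 4.5×ULN is acceptable is a clinical judgement outside this review.
- **The unconfirmed, unexplained case has no exit.** Section 9.8 contemplates resumption after interruptions of more than 72 hours for any reason, with notice to the medical monitor, and 9.9 allows discretionary withdrawal from study drug. What is missing is a stated criterion.
- **The primary analysis is put at risk, or the 250 mg arm especially.** No frequency is given, and the rule is the same in every arm. Interrupted subjects stay in the Full Analysis Set, and their earlier visits stay in the repeated-measures model.

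**Conclusion.** The point holds as a conflict of wording in a safety rule. Given an identified reversible cause, literal reading lets the restart laboratory condition and an interruption criterion be met together under either transaminase-only trigger when bilirubin is at most 2×ULN, and under the third trigger only if jaundice persists. It rests on reading *or* as written and on baseline values below the screening limits.

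A reader might infer that restart is open as soon as such a subject is interrupted. It is not: without an identified reversible cause, restart under this rule is unavailable, and a confirmed elevation with no convincing alternative cause means discontinuation.

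The effect on subjects or on the estimates cannot be sized from the documents. The point should be corrected because the text governs liver safety and the correction is cheap. The absent criterion for an unconfirmed, unexplained elevation is a secondary matter of missing detail, worth settling in the same edit.

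**What to change.** Reconcile the restart sentence in Protocol 9.8 with the three interruption criteria in the same section, so that no set of values satisfies both. The revised text should make clear how the two analytes combine and how jaundice is treated. In the same edit, state which path applies when the elevation is not confirmed and no cause is identified. The sponsor's clinical team should decide the clinical rule and the thresholds; this review takes no position on them.

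The cost is about two sentences in a protocol amendment or clarification letter. No new assessments are needed, and the sample size and planned analyses are unaffected.
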